13.2.3. Time and Events Table (Additional Years)

Study Visit (Weeks) ¹	4	8	12	16	20	24	28	32	36	40	44	48
Study Day	28 ±7d	56 ±7d	84 ±7d	112 ±7d	140 ±7d	168 ±7d	196 ±7d	224 ±7d	252 ±7d	280 ±7d	308 ±7d	336 ±7d
Efficacy Assessments												
Disease Activity Scales: SELENA SLEDAI, SLE Flare Index, and PGA ²						Х						Х
SLICC/ACR Damage Index												Х
Safety Assessments												
Symptom-driven Physical Exam						Х						Х
Record Concurrent Medications	Х	Х	Х	Х	Х	Х	Х	Х	Х	Х	Х	Х
Adverse Events	Х	Х	Х	Х	Х	Х	Х	Х	Х	Х	Х	Х
Vital Signs ^{3, 4}	Х	Х	Х	Х	Х	Х	Х	Х	Х	Х	Х	Х
Laboratory Assessments												
Haematology & Modified Chem 20 (non- fasting) ^{3, 5}						Х						Х
Urinalysis ^{5, 6}						Х						Х
Spot urine (protein to creatinine ratio) 3, 5, 6						Х						Х
Urine Pregnancy Test ^{3, 5, 7}	Х	Х	Х	Х	Х	Х	Х	Х	Х	Х	Х	Х
C3, C4, Anti-dsDNA Autoantibodies ^{3, 5}						Х						Х
IgG ^{3, 5, 8}												Х
IgA & IgM ^{3, 5, 8}												Х
Exploratory Lab Assessments												
Immunogenicity ^{3,9}						Х						Х
B cell Markers ¹⁰												Х
Investigational Product												
Belimumab Administration ^{4, 11}	Х	Х	Х	Х	Х	Х	Х	Х	Х	Х	Х	Х

- 1. Calendar represents a yearly (48-week) ongoing visit schedule until the subject is terminated from the study.
- 2. Guidelines for scoring proteinuria for SELENA SLEDAI are provided in protocol Section 6.3.1.1.
- 3. Assessments performed prior to dosing.
- 4. For any subject whose weight changes by more than 5% from that recorded at Day 0, use the weight at the current visit for calculating the belimumab dose to be administered.
- 5. During "Additional years", investigators can obtain any of the same laboratory assessments that are mentioned for Year 1 (haematology, modified Chem 20, urinalysis, spot urine to creatinine ratio, urine pregnancy, C3, C4, anti-ds DNA autoantibodies, IgG, IgA, and IgM), as unscheduled laboratory tests at any time during Year 2 and beyond, if clinically indicated. Any additional laboratory tests beyond this, if not related to the protocol, will be the responsibility of the investigator and subject.
- 6. A 24-hour urine may be done as an additional assessment if clinically indicated (e.g., renal flare).
- 7. Results of urine pregnancy tests in women of child-bearing potential must be available prior to belimumab dosing.
- 8. Serum immunoglobulin isotypes: IgG, IgM, IgA.
- 9. Immunogenicity testing includes quantifying the amount of belimumab present in the samples using the belimumab PK assay.
- 10. Biological Markers include FACS of peripheral lymphocytes: B lymphocytes (CD20+, CD20+/27+ memory, CD20+/27- naïve, CD20+/69+ activated, CD20+/138+ plasmacytoid, CD19+/27BRIGHT/38BRIGHT SLE subset and CD20-/138+ plasma cells).
- 11. After completion of the Week 48 visit during year 1 of the study, subjects in the treatment holiday and control groups can continue to receive belimumab therapy at 4-weekly intervals in the maintenance phase of this study. Subjects who withdraw from belimumab therapy during this maintenance phase will complete the Exit and follow-up visits detailed in the Year 1 Time and Events Table. The Exit visit Schedule should be scheduled 4 weeks after the final belimumab dose and the 16-week follow-up visit 16 weeks after the final belimumab dose.

13.3. Appendix 3: Assessment Windows

13.3.1. Mapping of the Maintenance Phase Visits for Subjects with an Escape Visit

In the eCRF, the next visit provided following the Escape visit is the Year 2 Week 8 visit, when chronologically the next visit would be the Year 2 Week 4 visit. Therefore, the maintenance phase visits for subjects with an Escape visit will be re-mapped in the ADaM analysis data sets to the maintenance phase visit, so that the visits align chronologically with those for subjects who complete the 52-week treatment phase and subsequently enter the maintenance phase.

	SDTM Variable	ADAM Variable							
Domain	VISITNUM VISIT	AVISITN AVISIT							
All	190 ESCAPE	190 ESCAPE							
All	220 YEAR 2 WEEK 8	210 YEAR 2 WEEK 4							
All	230 YEAR 2 WEEK 12	220 YEAR 2 WEEK 8							
All	240 YEAR 2 WEEK 16	230 YEAR 2 WEEK 12							
The mapping wi	The mapping will continue in this pattern for subsequent visits.								

If an Escape visit is present, mapping will occur as follows:

13.3.2. Mapping of Week 16 and 6-month Follow-up Visits

The 16-week and 6-month follow-up visits will be re-mapped in the ADaM analysis data sets so that they sort in chronological sequence when using the numeric visit number.

	SDTM Variable	ADAM Variable
Domain	VISITNUM VISIT	AVISITN AVISIT
All	170 16 WK FOLLOW-UP	9100 16 WK FOLLOW-UP
All	180 6 MO FOLLOW-UP	9200 6 MO FOLLOW-UP

13.3.3. Analysis Visit and Analysis Visit Number

The data are analyzed according to the planned visit assignment in the data.

Exit/withdrawal visits must be slotted to the appropriate planned visit according to the study phase. This will only be done for subjects that withdrew early and did not complete the 52-week treatment phase. Unscheduled laboratory visits will also be slotted to the appropriate planned visit.

The Analysis Visit is assigned based on the interval in which the Study Day for the exit/withdrawal visit or unscheduled laboratory visit falls according to intervals (inclusive) provided below. For completeness, the table also includes visits which are not slotted; these visits will have 'na' for 'not available' listed for the Interval Start and End Day.

	Analysis		Interval Start Day	Interval End Day
Analysis Visit	Visit Number	Target Study Day ¹		_
Screening	10	-34	na	na
52-week Treatment	Phase visits:			
Baseline	20	1	na	na
Week 4	30	29	22	42
Week 8	40	57	43	70
Week 12	50	85	71	98
Week 16	60	113	99	126
Week 20	70	141	127	154
Week 24	80	169	155	182
Week 28	90	197	183	210
Week 32	100	225	211	238
Week 36	110	253	239	266
Week 40	120	281	267	294
Week 44	130	309	295	322
Week 48	140	337	323	350
Week 52	150	365	351	378

	Analysis		Interval Start Day	Interval End Day				
Analysis Visit	Visit Number	Target Study Day ¹						
¹ Day 0 visit date in study 116027 = Study Day 1.								

13.3.4. Windows for Assessment of Post-injection/infusion sensitivity reactions (PISR) and hypersensitivity reactions (HSR)

The windows for assessment of PISR/HSR, as described in the AESI definitions in Section 13.9.2, are as follows:

Date of Infusion								
Day 1	Day 2	Day 3						
SMQ narrow, broad and algorithmic searches (On day of injection/infusion or within 3								
days of injection/infusion)								

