- 12. Pharmacokinetic sampling at select sites for subjects in the control and treatment holiday groups; subjects in the treatment holiday group can have PK sampling performed at any time during the visit between Weeks 0 and 16. Otherwise, if on a dosing day, sampling must be performed **prior** to dosing. Collect blood samples pre-dose and post-dose at the end of the infusion at Weeks 24 and 52 (or earlier if belimumab is re-started before Week 24 in the event of a severe flare by using the escape option). Subjects in the long-term discontinuation group will have one PK sampling performed at any time during the visit between Weeks 0 and 24. PK sampling for the long-term discontinuation group is not performed after Week 24. Long-term discontinuation subjects withdrawing before Week 24 will have one PK sampling performed at any time during the EXIT visit. PK sampling for long-term discontinuation subjects withdrawing after Week 24 is not performed at the EXIT visit.
- 13. Blood sample for immunogenicity will be taken at Weeks 12, 24, 36 and 52 for all three groups. In addition, a blood sample for immunogenicity will also be taken 4 weeks prior to the reintroduction of belimumab (at Week 20 since belimumab will be reintroduced at Week 24) in the treatment holiday group. A blood sample for immunogenicity must be taken at least 6 months after the final dose of investigational product for any subjects in the control group or treatment holiday group who had an anti-belimumab antibody response at the 16-week follow-up visit (or at the last immunogenicity assessment if 16-week follow-up is not available). Note that serum samples for immunogenicity must be collected pre-dose at the time of dosing from subjects in the treatment holiday group who experience a severe flare prior to Week 24 and consequently receive open-label belimumab as rescue. Immunogenicity blood sample will not be collected at the 6-month follow up visit for subjects in the long-term discontinuation group as this visit does not apply to this subject group.
- 14. Measured in treatment holiday group at Weeks 16 and pre-dose at Week 24. Measured in long-term discontinuation group at Weeks 16, 24 and 32. Not measured in control group.

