7.2.2.3. Rebound

The frequencies and percentages of subjects who rebound will be presented by visit through the Week 24 visit, and at any time during the first 24 weeks.

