13.4.1.1. Treatment Holiday Group

Endpoint	Day 0 Visit Parent Study	Day 0 Visit BEL116027 Study	Week 24/ TX Re-start Visit	Week 52/ Exit/Escape Visit	Week 16 Follow- up Visit	
		Baseline				
Flare, PGA, Prednisone,	N1/A	52-Week Trea	atment Phase	Maintenance		
SLICC	N/A	Holiday Phase	Re-start Phase	Phase	N/A	
	I	Baseline			1	
SS, Auto-antibodies	Pre-Study	52-Week Trea	atment Phase	Maintenance	N1/A	
Immunoglobulins, B-cells [1], BLyS	Phase	Holiday Phase	Re-start Phase	Phase	N/A	
		Baseline	1		1	
Rebound [2]	Pre-Study	52-Week Trea	atment Phase			
	Phase	Holiday Phase	N/A	N/A	N/A	
	L	Baseline			1	
Adverse Events, Lab		52-Week Trea	atment Phase	Maintenance		
Parameters, Vital Signs, Con Meds Immunogenicity [1]	N/A	Holiday Phase	Re-start Phase	Phase	N/A	

N/A = Not Applicable.

[1] Immunogenicity and B-cells may also be collected at the 6-month follow-up visit. The 6-month follow-up visit is not represented in the diagram since it does not define a treatment phase of the study.

[2] Rebound is only assessed up to the Week 24/Treatment re-start visit.

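### The Escape visit has no planned analysis week, and the SAP does not say whether it feeds the carry-forward of disease-activity scores

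*SAP*

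**What the plan says.** SAP 13.3.3 (Analysis Visit and Analysis Visit Number) gives the slotting rule: "Exit/withdrawal visits must be slotted to the appropriate planned visit according to the study phase". It then limits it: "This will only be done for subjects that withdrew early and did not complete the 52-week treatment phase". Unscheduled laboratory visits are slotted as well. Of the window table it says: "For completeness, the table also includes visits which are not slotted". The rows run from Screening and Baseline through Week 4 to Week 52, and Escape is not among them, slotted or unslotted.

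SAP 13.3.1 deals with Escape only to repair the visit sequence that follows it. In the eCRF, "the next visit provided following the Escape visit is the Year 2 Week 8 visit", so "the maintenance phase visits for subjects with an Escape visit will be re-mapped in the ADaM analysis data sets to the maintenance phase visit". Escape itself stays as 190 ESCAPE in all domains.

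SAP 13.4.1.1 closes the holiday group's 52-week phase with a column headed "Week 52/ Exit/Escape Visit". SAP 13.4.1 places an assessment made on a phase cut-point date, other than Day 0, in the phase before it. It adds that a subject who restarts before Week 24 has no Re-start phase.

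For rebound, SAP 7.2.2.3 states that "subjects who rebound will be presented by visit through the Week 24 visit", and adds a row for rebound at any time in the first 24 weeks.

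Protocol Table 2, footnote 13, requires a sample at rescue: "serum samples for immunogenicity must be collected pre-dose at the time of dosing from subjects in the treatment holiday group" when they have a severe flare before Week 24 and receive belimumab.

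**The concern.** Escape is an outcome-driven visit. Protocol 3.1 ties it to a severe flare, and Protocol 4.4 also allows it when the subject's condition worsens. Only the holiday group can have one. If data from that visit drop out of the Week 4 to Week 24 rows, the by-visit picture of the holiday loses observations exactly where the holiday failed. The outputs concerned are SELENA SLEDAI rebound by visit (Table 2.6, a headline display), SELENA SLEDAI change (Table 2.7, Figure 2.3), PGA change (Table 2.8), antibody response by visit (Table 3.51), and the laboratory, vital-sign and biomarker summaries.

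A subject in any group who withdraws early has the exit visit placed in a planned week. A holiday subject who escapes on the same study day does not. The study is descriptive and exists to report on treatment holidays and rebound, so a one-sided gap in these tables matters even though no test depends on it.

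**Working it through.** There is no stated figure to reproduce: the study has no power calculation and the documents report no escape count. The check is a trace of the rules, followed by an illustration.

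**Does Escape reach a planned week?**

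1. An escaper enters the maintenance phase (Protocol 3.1 and 4.4).
2. SAP 13.6.2 counts a subject as withdrawn from the 52-week phase only if there are no maintenance visits. An escaper with a maintenance visit is therefore not an early withdrawal, and the condition in 13.3.3 is not met.
3. SAP 13.3.1 leaves the record at 190 ESCAPE, and the window table has no row for it.
4. Under the cut-point rule in 13.4.1, Escape-day assessments fall in the Holiday Phase.

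The record is therefore in the Holiday Phase and in no planned week.

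**What follows for each kind of output?**

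- *Observed data only.* Laboratory tests (8.3.4), immunogenicity (8.4.4.1), vital signs (8.4.4.2) and biomarkers (11.1.4) are not imputed. Their by-visit rows omit whatever was taken at Escape.
- *LOCF.* SELENA SLEDAI and rebound (7.2.4.2) and PGA (7.3.4.1) are carried forward. SAP 13.7.2 takes the source to be the last earlier non-missing on-treatment value. It does not limit the source to planned visits, does not mention Escape, and does not say whether a holiday subject who is off belimumab counts as on-treatment. Nor does it say whether the weeks after escape are filled at all.
- *Not defined by visit slot.* Time to first flare and to first severe flare run to the event date (7.1.2, 7.2.2.2). Any-time rebound runs up to the re-start visit (7.2.2.3; 13.4.1.1, note 2). Antibody response is also summarised at any time after baseline (8.4.2.1).

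**Illustration for the LOCF scores.** From the documents: 12 holiday subjects enrolled (SAP 2.3). Assumed: k escapers, each with Escape score e; every other score, including the escapers' last planned score, averages m = 2.

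- LOCF from the Escape record: mean = ((12 − k) × m + k × e) / 12
- LOCF from planned visits only: mean = m = 2.00
- Weeks after escape not filled: mean = 2.00, on 12 − k subjects
- Gap between the first reading and the other two: k × (e − m) / 12

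| k | e | Mean using Escape | Gap |
|---|---|---|---|
| 0 | – | 2.00 | 0.00 |
| 1 | 6 | (11×2 + 1×6)/12 = 2.33 | 0.33 |
| 2 | 10 | (10×2 + 2×10)/12 = 3.33 | 1.33 |
| 3 | 10 | (9×2 + 3×10)/12 = 4.00 | 2.00 |
| 4 | 14 | (8×2 + 4×14)/12 = 6.00 | 4.00 |

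Each escaper is 1/12 = 8.3% of the group. A by-visit rebound row moves by that much only for an escaper whose Escape score exceeds the parent-study baseline.

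**Would the existing windows take Escape?** Day 60 falls in Week 8 (Days 43–70), Day 100 in Week 16 (99–126), Day 150 in Week 20 (127–154) and Day 168 in Week 24 (155–182). The first window opens on Day 22, so an Escape on Days 2 to 21 has none.

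**The case against.** The strongest case is that a reader may infer too much: that Escape holds a holiday subject's worst scores, and that the by-visit holiday results necessarily leave the worsening out. The documents do not support either statement in full.

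- The LOCF text is wide enough to take in the Escape record. If it does, the worsening enters the SELENA SLEDAI, rebound and PGA rows from the next planned week onward. This stands: for those scores the defect is an unspecified rule, not a demonstrated omission. One detail points the other way. SAP 13.3.2 renumbers the follow-up visits so that they sort chronologically by visit number, whereas Escape keeps 190, after Week 24 (80) and Week 52 (150). Carry-forward run in visit-number order would not reach it. That is an inference about programming, not a stated rule.
- No schedule lists an Escape visit or its assessments. Only the pre-dose antibody sample and the PK samples are specified for early re-start. If the flare is found at a planned four-weekly visit, its scores may already sit in a planned row. This also stands.
- The severe-flare and any-time summaries do not depend on slotting, and individual listings of flares, SELENA SLEDAI, PGA, antibodies and biomarkers are planned. The worsening is not hidden from the report as a whole.
- Unscheduled visits are left out of summary tables in every group (13.5.2), so other groups can lose scores too. That is a separate rule; the absence of a slot for Escape still touches holiday subjects alone.
- The column heading that groups Exit with Escape might suggest that Escape is slotted as an exit visit. This is weak against the explicit 190 mapping and the early-withdrawal condition.

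**Conclusion.** The point holds in this form: Escape data have a phase but no planned week. Observed-only by-visit rows omit them, and the SAP leaves their role in LOCF undefined. If LOCF uses planned visits only, the value from before the worsening stands through Week 24. Because escape follows worsening and early withdrawals' exit visits are slotted, the gap tends to favour the holiday.

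The size is unknown. It is zero if nobody escaped, and each escaper is 8.3% of 12 subjects. The shifts of 0.33 to 4.00 points shown for one to four escapers rest on assumed scores and indicate scale only. Rebound need not follow from escape. BEL113750 enrolled at SELENA SLEDAI 8 or more, and holiday subjects enter at 3 or less. A subject from that study still at 3 or less who rises by 6 points reaches at most 9, which exceeds a parent baseline of 8 but no higher one. Severe flare in this study also excludes flares triggered only by the score passing 12, so escape need not involve a large rise.

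The primary endpoint is not affected.

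**What to change.** In SAP 13.3.3, slot the Escape visit by study day into the existing 52-week windows, as for exit visits, for all assessments taken there. Add a rule for Days 2 to 21, which have no window, and say how a display handles an Escape sample that lands in a week with no scheduled row for that test.

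In 7.2.4.2, 7.3.4.1 and 13.7.2, name Escape as an eligible LOCF source through Week 24 for SELENA SLEDAI, rebound and PGA, and clarify what on-treatment means for a subject on holiday. Carrying an Escape score forward after belimumab has restarted is a choice of estimand, so state it as one. In 7.2.2.3, state that any-time rebound includes the Escape visit.

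Where a planned visit already sits in the same window, apply one pre-stated rule consistent with 13.6.1, which averages multiple measurements at a time point. Do not substitute the Escape value automatically: that would replace a planned measurement with an outcome-selected one in a single group.

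The cost is a few lines of SAP text and one analysis-dataset derivation, with no new data. Reporting the number of escapers by visit beside these tables would let readers judge the effect.

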13.4. Appendix 4: Study Phases and Treatment Emergent Adverse Events

13.4.1. Treatment Phases

- Visits, assessments and events will be classified according to the time of occurrence relative to the following cut-point dates for each treatment group.
- For convenience and ease of data presentation, the 52-Week Treatment Phase has the same name designation for all three treatment groups, even though the LTC group does not receive treatment at all during this phase and the TH group receives treatment for only the second half of the phase.
- Only the TC and TH groups are eligible to participate in the Maintenance Phase.
- If an AE start date falls on the Day 0 date, then it will be considered treatment emergent (i.e., fall in the 52-week treatment phase). If a concomitant medication start date falls on the Day 0 visit date, the concomitant medication will be considered to fall in the 52-week treatment phase. Any other assessments that fall on the Day 0 visit date will be considered to occur in the pre-study phase.
- For the TC group, if the first infusion date differs from the Day 0 visit date, then the first infusion date will be used as the phase cut-point.
- Other than Day 0, if an assessment or event occurs on the same date as a phase cutpoint, then the event will be considered to fall in the previous phase. For example, if a new prednisone dose starts on the same date as the Week 24 visit date and then continues for a total of 7 days, then the first day of that prednisone dose will fall into the Holiday Phase and the remaining 6 will fall into the Re-start phase.
- For AEs, if the AE Onset date is missing, then the AE will be considered to occur in the 52-week treatment phase.
- For the TH group, a subject who re-starts treatment prior to Week 24 will not have a Re-Start phase.

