Subjects in the treatment holiday group are anticipated to be temporarily withdrawn from belimumab treatment for the initial 24 week holiday period of this study but therapy with belimumab 10 mg/kg can be reintroduced before the Week 24 visit if the subject's condition worsens or meets the definition of a severe flare as per the SLE flare index (Appendix 1). Subjects in the treatment holiday group who re-start belimumab treatment before the end of the 24-week holiday period will escape to the maintenance part of this study to receive further belimumab therapy.

The investigator must make every reasonable attempt to re-start belimumab therapy at the Week 24 visit. Any subject in the treatment holiday group who remains off-therapy with belimumab at the Week 24 visit can still be treated with belimumab from Week 28 onwards.

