8.2.1.2. Post-infusion systemic reactions by infusion

For the TH group in the RS phase, summaries of post-infusion systemic reactions will be presented by the first six infusions in the RS phase and PT for the following categories:

- Post-Infusion Systemic Reactions per Anaphylactic Reaction CMQ broad search (on the day of the infusion or within 3 days after the infusion)
- Serious Post-Infusion Systemic Reactions per Anaphylactic Reaction CMQ broad search (on the day of the infusion or within 3 days after the infusion)
- Serious Acute Post-Infusion Systemic Reactions/Hypersensitivity per GSK adjudication
- Serious Delayed Acute Hypersensitivity Reactions per GSK adjudication
- Serious Delayed Non-Acute Hypersensitivity Reactions per GSK adjudication

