Y	'Y' if CMSCAT ne blank and the route of administration is "INTRADERMAL" "PO" "INTRAMUSCULAR", "INTRAVENOUS", "ORAL", or "SUBCUTANEOUS"
Ν	'N' otherwise and CSMCAT ne blank

Treatment Compliance

• Treatment compliance for patients completing the 52 week treatment phase or withdrawals is calculated as:

treatment compliance (%)

- $= 100 \times \frac{Number \ of \ infusions \ prescribed Number \ of \ infusions \ missed}{Number \ of \ infusions \ prescribed}$
- Prescribed number of infusions will be 7 for the TH arm and 13 for the TC arm, except for TH subjects who escape to the Maintenance Phase. For TH subjects who escape, the treatment compliance will be missing. The Week 52 infusion is considered to be the first infusion of the maintenance phase.
- NB: for withdrawals the number of infusions prescribed is the number from Day 0 up to the withdrawal date

Extent of Exposure

Number of days of exposure to study treatment during the 52-week Treatment Phase will be calculated based on the formula:

Duration of Exposure in Days = (Date of last infusion in BEL116027 52-week treatment Phase– Date of first infusion in BEL116027) + 28

- The Week 52 infusion is considered to be the first infusion in the Maintenance Phase, and will not be considered in this calculation.
- Subjects who were enrolled in the TH and TC groups but did not receive an infusion will be categorised as having zero days of exposure.
- Exposure will not be calculated for the LTD group.
- Only complete dates will be used when calculating duration of exposure.
- Exposure will not be adjusted for skipped infusions.

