For CSR reporting, all post-infusion systemic reaction AESIs defined via narrow, broad, or algorithmic search, the AEs need to have occurred on the day of an infusion/injection or within 3 days after an infusion/injection. See Section 13.3.4 for the definition of the 3-day assessment window. GSK will review all serious events identified via the broad search occurring within 21 days after an infusion/injection, and adjudicate these events as post-infusion systemic reactions or hypersensitivity reactions per the criteria in Section 13.9.10.2. Adverse events with partial or missing start dates will be included unless there is evidence through comparison of partial dates to suggest otherwise.

Sampson Criteria

Sampson et al define anaphylaxis as a severe, potentially fatal, systemic allergic reaction that occurs suddenly after contact with an allergy-causing substance. In addition, one of the following 3 criteria must be met: (1) acute onset of illness with involvement of skin or mucosal tissue, accompanied with either respiratory compromise, reduced blood pressure, or hypotension-related symptoms of end-organ dysfunction (2) reduced blood pressure associated with a known allergen or (3) two or more of the following that occur rapidly after exposure to an allergen: a) involvement of skin-mucosal tissue b) respiratory compromise c) reduced blood pressure d) persistent GI symptoms.

With the exception of GI symptoms, all symptoms required to assess anaphylaxis per Sampson criteria would be identified by Broad Anaphylaxis SMQ or the Anaphylactic Reaction SMQ algorithmic. Therefore, any events falling under the below criteria will be adjudicated by GSK prior to database release to determine if serious anaphylaxis per Sampson criteria is met.

Possible cases of serious anaphylaxis per Sampson criteria will be identified as follows:

a. Any Infusion/Injection-related Reaction per Anaphylactic Reaction SMQ broad

search SAE which occurs on the day of an injection.

- b. Any AE or SAE in the "Gastrointestinal disorders" SOC that occurs on the day that criterion in a) above is met.
- c. Any anaphylaxis and hypersensitivity reactions per Anaphylactic Reaction SMQ algorithmic search SAE which occurs on the day of an infusion/injection.

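### Same-day reactions to the first re-introduction infusion are flagged as off-drug, and the only by-infusion re-exposure table leaves out subjects who re-start before Week 24

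*SAP*

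**What the plan says.** SAP 13.4.1 assigns events to phases by cut-point date. Day 0 has its own treatment; on any other cut-point date the rule reads in part: "occurs on the same date as a phase cutpoint, then the event will be considered to fall in the previous phase". The worked example is a seven-day prednisone course starting on the Week 24 date: one day goes to Holiday and six to Re-start. For the treatment holiday (TH) group, the diagram in 13.4.1.1 sets the Holiday/Re-start cut-point at the "Week 24/ TX Re-start Visit" and lists adverse events among the data split there.

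SAP 8.2.1.2 plans a re-exposure display: "summaries of post-infusion systemic reactions will be presented by the first six infusions in the RS phase". Its search categories cover reactions "on the day of the infusion or within 3 days after the infusion". SAP 13.9.2 repeats this for the clinical study report: "the AEs need to have occurred on the day of an infusion/injection or within 3 days after an infusion/injection". The display is Table 3.22, whose title confines it to the TH Re-start phase.

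For compliance, SAP 13.6.2 states: "The Week 52 infusion is considered to be the first infusion of the maintenance phase". That infusion is given on a cut-point date and is assigned forward.

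On early re-start, SAP 13.4.1 says that "a subject who re-starts treatment prior to Week 24 will not have a Re-Start phase". Protocol 4.4 says that TH subjects "who re-start belimumab treatment before the end of the 24-week holiday period will escape to the maintenance part of this study".

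**The concern.** There are two problems.

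**Conflicting rules.** The first re-introduction infusion is given at the visit that defines the cut-point. A reaction that day is Holiday (off-drug) under 13.4.1 but belongs to that infusion under 8.2.1.2 and 13.9.2. The only same-date exception for adverse events in the TH group is Day 0. The affected day is the core of the window: SAP 13.9.10.2 generally applies onset within 24 hours to post-infusion reactions and classes hypersensitivity as acute at onset of one day or less.

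**Omission.** Early re-starters have no Re-start phase, and Table 3.22 covers only that phase. It is the only by-infusion display of re-exposure, and it cannot contain them.

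Tolerability of belimumab after a drug-free interval is a main safety question in a treatment-holiday study. Protocol 6.4.12 asks for three hours of supervision after the first two re-start infusions, for rescue re-starts and Week 24 re-starts alike. As written, two programmers could produce different infusion 1 rows, and the subjects who re-started because their disease worsened would be missing.

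**Working it through.** **Inputs**
- Cut-point rule and prednisone example: SAP 13.4.1. Cut-point visit: SAP 13.4.1.1. Week 24 target study day 169: SAP 13.3.3.
- Prescribed infusions in the 52-week phase, 7 (TH) and 13 (control): SAP 13.6.2.
- TH subjects enrolled, 12: SAP 2.3.
- Infusion-day reactions in earlier studies, 17% on belimumab and 15% on placebo: protocol 6.4.12.
- Not in the documents: the per-infusion risk and the number of early re-starters. Both are assumptions below.

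**1. Reproduce the plan's figures.** Classify study day ≤ 169 as Holiday and later days as Re-start. A course over days 169 to 175 gives 1 Holiday day and 6 Re-start days, as in the SAP. Infusions every four weeks: (48 − 24)/4 + 1 = 7 for TH and (48 − 0)/4 + 1 = 13 for control. Both agree with the SAP.

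**2. Apply the rule to the first re-introduction infusion on day 169.**

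| Day | Relation to infusion | Phase flag | In the 8.2.1.2 window |
|---|---|---|---|
| 169 | same day | Holiday | yes |
| 170 | +1 | Re-start | yes |
| 171 | +2 | Re-start | yes |
| 172 | +3 | Re-start | yes |

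One of the four window days carries the wrong flag. The flare follow-up formulas in SAP 13.6.3 show the same convention: the re-start date counts in TH-phase time and not in RS-phase time.

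**3. What infusion 1 in Table 3.22 can mean.**
- The window governs: infusion 1 is Week 24, with all four days; the first six are Weeks 24 to 44.
- Events are filtered on the phase flag and infusions are assigned forward, by analogy with the Week 52 rule: infusion 1 is Week 24, but its same-day reactions are missing.
- The cut-point rule is applied to the infusion as well: Week 24 becomes Holiday, leaving (48 − 28)/4 + 1 = 6 infusions, Weeks 28 to 48, and the first re-exposure drops out.

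Nothing in the SAP chooses between these.

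**4. Early re-starters.** They have no Re-start phase, so they contribute no rows to Table 3.22. Their Escape visit is itself a cut-point (13.4.1.1). A reaction on that date goes back to Holiday and is counted in the 52-week tables; later reactions fall in Maintenance. Adverse event Tables 3.4 to 3.21 are all titled for the 52-week phase, so the later reactions reach only listings and subject profiles (SAP 8.5).

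**5. Size of the first point.** Expected subjects = 12p; P(at least one) = 1 − (1 − p)^12; one subject = 1/12 = 8.3 percentage points.
- p = 1% (assumed): 12 × 0.01 = 0.12; 1 − 0.99^12 = 0.11.
- p = 10% (assumed): 12 × 0.10 = 1.2; 1 − 0.90^12 = 0.72.
- Loose upper figure: 12 × 0.17 = 2.04. The 17% covers all infusions in earlier studies, not one, and placebo at 15% gives 1.80.

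**6. Size of the second point.** With k early re-starters, the omitted share is k/12 and up to 6k of 6 × 12 = 72 first-six infusions are lost, if every subject receives six.

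| k (assumed) | Subjects left | Omitted | Infusions omitted, up to |
|---|---|---|---|
| 0 | 12 | 0% | 0 |
| 1 | 11 | 8.3% | 6 |
| 2 | 10 | 16.7% | 12 |
| 3 | 9 | 25.0% | 18 |

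**The case against.** The best reply to the first point is that the specific rule should override the general one. The post-infusion window is stated twice and includes the infusion day, whereas the cut-point bullet is generic and its example concerns prednisone. Stripping same-day events from infusion 1 can hardly be intended. How the table is keyed may also be settled in the Program Safety Analysis Plan, which SAP 13.9 names as the primary source for these events, or in the display shells, which are available only on request. This reading is plausible, but it is not written down. SAP 8.2.1.2 itself limits the display to infusions in the RS phase, and 13.4.1.1 applies the phase split to adverse events by name.

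On the second point, the SAP is open that early re-starters lack a Re-start phase. Their drug-free intervals are shorter and vary, so pooling them with Week 24 re-starters is a matter of presentation. That supports a separate column; it does not justify leaving them out.

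The mitigating facts stand. Same-day reactions remain in Table 3.21. The adverse event and infusion-reaction listings carry no phase restriction in their titles. Reactions from the day after infusion are unaffected for Week 24 re-starters, as are those subjects' 52-week totals. The study is descriptive, so no inference changes.

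**Conclusion.** Both points hold. The first is a conflict between written rules. It loses data from Table 3.22 only if the table is filtered on the phase flag, or if the Week 24 infusion is itself classed as Holiday. The second needs no disputed reading: the table cannot include anyone who re-starts before Week 24.

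The effect is on attribution and completeness of one safety table, not on what the report contains overall. In absolute terms it is small, about 0.1 to 1.2 subjects at an assumed 1% to 10% same-day risk. In a group of 12, however, each subject moves a percentage by 8.3 points. The omission ranges from nothing (no early re-starters) to a quarter of the group (three, assumed). Because this is the plan's only by-infusion view of re-exposure, it should be settled before the table is produced.

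**What to change.** 1. Resolve the conflict in SAP 13.4.1 in one of two ways. Either state that Table 3.22 follows the 8.2.1.2 infusion window whatever the phase flag, or assign adverse events with onset on the date of the first re-introduction infusion to Re-start, using onset time to separate pre-dose events where it is collected.
2. Define re-start infusion 1 as the first belimumab infusion in BEL116027 for any TH subject.
3. Include the first six re-start infusions of early re-starters in Table 3.22, in a separate column if preferred, and state the denominator for each column.

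The cost is a few sentences of SAP text, one line of phase-derivation code and one column. The first option in step 1 needs no new data: the treatment-state table in SAP 13.4.1.3 already uses the date of first infusion in this study to derive adverse event onset for TH subjects. The onset-time option depends on whether event times are collected, which the documents do not show. The downside is that, without onset times, some pre-dose events on the infusion date will count as Re-start; these should be footnoted.
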